9.1. Sample Size Determination

For Parts 1 and 2, the sample size of approximately 56 healthy subjects (up to 80 if separate multiple dose cohorts are needed) and up to approximately 35 patients with CRSwNP, for a total of up to approximately 91 subjects (up to 115 with separate multiple dose cohorts), was based on the clinical considerations to provide safety, tolerability information and pharmacological considerations and on the desire to minimize exposure to healthy subjects at each dose level. Early withdrawals may be replaced to ensure sufficient subjects at each dose level to adequately assess safety and PK information and to provide a placebo group

comparison group. No formal statistical testing will be applied to the safety, PK data.

For Part 3, the sample size of approximately 20 subjects with moderate to severe AD was based on the clinical considerations to provide safety, tolerability, and information, and on the desire to minimize exposure to AD subjects before the safety and tolerability of PF-06817024 in subjects with AD is established. Additional subjects up to a total of approximately 32 will be

Early withdrawals may be replaced to ensure sufficient subjects at each dose level to assess safety, PK information adequately and to provide a placebo group comparison group. No formal statistical testing will be applied to the safety, PK or

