8.1.8. Vital Signs Data

Absolute values and changes from baseline in supine systolic and diastolic blood pressure and pulse rate will be summarized by study part (SAD/MAD, Nasal Polyps, Atopic Dermatitis). They will be further summarized by cohort, treatment and time postdose, according to sponsor reporting standards as appropriate. Tables will be paged by parameter. Baseline is as defined in Section 6.2.3.

Mean changes from baseline for supine systolic and diastolic blood pressure and pulse rate will be plotted against time postdose. On each plot there will be 1 line for each cohort. Data from all cohorts will be plotted on the same figure using separate lines for the 2 placebos. Corresponding individual plots of changes from baseline will also be produced for each cohort and treatment.

For supine systolic and diastolic blood pressure and pulse rate, the differences between each dose and placebo (dose – placebo) will be summarized (N, mean, 90% confidence interval) and plotted (mean) for each cohort, dose and timepoint (including baseline).

Maximum absolute values and changes from baseline for vital signs will also be summarized descriptively by treatment using categories as defined in Appendix 1. Numbers and percentages of subjects meeting the categorical criteria will be provided. All planned and unplanned postdose timepoints will be counted in these categorical summaries. All values meeting the criteria of potential clinical concern will be listed.

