8.1.9. ECG Data

Absolute values and changes from baseline in QT, heart rate, QTcF, PR and QRS will be summarized by study part (SAD/MAD, Nasal Polyps, Atopic Dermatitis). They will be further summarized by cohort, treatment and time postdose using sponsor reporting standards as appropriate. Tables will be paged by parameter. Baseline is as defined in Section 6.2.4. All triplicate measures will be averaged prior to summarization. Telemetry data will not be summarized along with other ECG data but listed in adverse events as appropriate.

Mean changes from baseline in QT, heart rate and QTcF will be plotted against time postdose. On each plot there will be 1 line for each treatment. Data from all cohorts will be plotted on the same figure using separate lines for the 2 placebos. Corresponding individual plots of changes from baseline will also be produced for each cohort and treatment.

Changes from baseline in QTcF will also be plotted separately against drug concentrations. This will be a scatter plot for all observations where QTcF and drug concentration are recorded. Placebo data will also be included (with drug concentration set to zero). Different symbols will be used for each cohort. There will be 1 plot for each of the parts of the study (Part 1, 2, 3), for Part 1 the SAD and MAD data will be plotted separately. Maximum increase from baseline (0 to 12 hours) for QTcF, heart rate, QT, PR and QRS will be summarized by cohort and treatment, according to sponsor reporting standards for the first two parts (SAD/MAD and Nasal Polyps) of the study.

In addition for QTcF, heart rate and QT, and change from baseline for each subject will be summarized and plotted (N, mean, 90% confidence interval) for each cohort, dose and timepoint (including baseline).

ECG endpoints and changes from baseline (QTcF, PR and QRS) will also be summarized descriptively by cohort and treatment using categories as defined in Appendix 1 (for QTc these correspond to ICH E141).¹ Numbers and percentages of subjects meeting the categorical criteria will be provided. All planned and unplanned postdose timepoints will be counted in these categorical summaries. All values meeting the criteria of potential clinical concern will be listed.

Listings of subjects with any single postdose value \geq 500 msec will also be produced for QTcF.

QTcB will be listed only and not summarized.

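### SAP 8.1.9 puts its ECG 90% intervals on within-arm change only; add the dose-minus-placebo contrast that SAP 8.1.8 already gives for blood pressure and pulse

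*SAP*

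**What the plan says.** **ECG intervals.** SAP 8.1.9 says: "In addition for QTcF, heart rate and QT, and change from baseline for each subject will be summarized and plotted". The display is "N, mean, 90% confidence interval) for each cohort, dose and timepoint (including baseline". No dose-minus-placebo quantity is defined for any ECG parameter.

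**Vital signs intervals.** For supine blood pressure and pulse rate, SAP 8.1.8 says "the differences between each dose and placebo (dose – placebo) will be summarized (N, mean, 90% confidence interval) and plotted (mean", again by cohort, dose and time point.

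**How placebo enters the ECG section.** Three displays in SAP 8.1.9 carry it:
- Values and changes: "They will be further summarized by cohort, treatment and time postdose using sponsor reporting standards as appropriate".
- Mean-change plots: "Data from all cohorts will be plotted on the same figure using separate lines for the 2 placebos".
- QTcF against concentration: "Placebo data will also be included (with drug concentration set to zero".

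**Baseline.** SAP 6.2.4 uses the mean of the Day 1 pre-dose triplicates in Part 1 and the last value before first dose in Parts 2 and 3. Protocol 9.6.1 also allows a time-matched Day 0 baseline, but Schedule of Activities Table A has no Day 0 ECG.

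**Role of placebo.** Protocol 9.1 allows withdrawals to be replaced partly "to provide a placebo group comparison group".

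**The concern.** Clinically relevant ECG change is a primary endpoint (Protocol 2.2.1). A within-arm change from a pre-dose baseline is the drug effect plus anything else that moves the ECG after that baseline.

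In Parts 1 and 2 the dosing day offers several such influences. Subjects are fasted and dosed at about 08:00, give or take 4 hours (Protocol 5.4.3). They are confined to the procedure room for the first 4 hours (4.3.1.3). Lunch may come from 2 hours and dinner at about 7 to 8 hours after the start of dosing (4.3.1.1). Day 1 post-dose ECGs fall at 1, 2, 8 and 12 hours (Tables A and D). With no time-matched baseline, concurrent placebo is the only control for these influences.

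A positive shift could look like a drug effect, and a negative one could hide a real effect. The section that subtracts placebo and the section that does not sit next to each other, and the SAP gives no reason for the difference.

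**Working it through.** **1. Which quantity carries the interval.** Apart from the parameters covered, the 8.1.8 and 8.1.9 sentences share the same statistics (N, mean, 90% interval) and the same closing breakdown. Only 8.1.8 names a difference from placebo. Two features suggest that 8.1.9 is damaged. The list of parameters runs into a stray conjunction. It also asks for an interval at baseline, where change from baseline is zero for every subject.

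**2. Could a shared shift matter?** The documents give neither the SD of QTcF change nor any non-drug shift. I assume an SD of 10 ms (range 8 to 12), no drug effect, and a shift common to active and placebo. The chance that a within-arm 90% interval excludes zero comes from a noncentral t with n − 1 degrees of freedom and noncentrality (shift/SD)·√n:

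| n | shift 0 ms | shift 5 ms (SD 12 to 8) | shift 10 ms (SD 12 to 8) |
|---|---|---|---|
| 6 | 0.10 | 0.28 (0.23 to 0.38) | 0.68 (0.55 to 0.84) |
| 21 | 0.10 | 0.72 (0.58 to 0.87) | above 0.97 |

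A dose-minus-placebo interval stays at 0.10 because the shared shift cancels.

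**3. What the correction costs in precision.** The plan states no ECG precision figure to reproduce. Half-widths in SD units, assuming equal variances, are:
- within arm: t(0.95, n−1)/√n
- difference: t(0.95, n1+n2−2)·√(1/n1+1/n2)

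Inputs:
- *Part 1 IV*: 6 active per cohort. Pooled placebo is 5 IV cohorts × 2 = 10, because SAP 2.1 says escalation stopped before Cohort 6.
- *Part 1 SC (Cohort 7)*: 6 active, 2 placebo.
- *Part 2*: 20 subjects dosed (Protocol 1.2.5.1) and 11 in the active PK column (Protocol Table 1), so 20 − 11 = 9 placebo. This is inferred.
- *Part 3*: 28 enrolled (SAP 2.3), randomized 2:1 and later 3:1. All at 3:1 gives 21 vs 7; all at 2:1 gives about 19 vs 9.

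Worked examples:
- 6 within arm: 2.015/√6 = 0.82.
- 6 vs 10: 1.761 × √(1/6+1/10) = 0.91.
- 6 vs 2: 1.943 × √(1/6+1/2) = 1.59.

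| Comparison | Within arm | Dose − placebo |
|---|---|---|
| Part 1 IV, 6 vs 10 pooled | 0.82 | 0.91 |
| Part 1 SC, 6 vs 2 | 0.82 | 1.59 |
| Part 2, 11 vs 9 | 0.55 | 0.78 |
| Part 3, 21 vs 7 | 0.38 | 0.74 |
| Part 3, 19 vs 9 | 0.40 | 0.69 |

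At the assumed SDs of 8 to 12 ms, the difference half-width is about 7 to 11 ms for Part 1 IV (0.91 × 8 to 0.91 × 12) and 13 to 19 ms for the SC cohort (1.59 × 8 to 1.59 × 12).

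**The case against.** The strongest reply is that the study draws no conclusion from these intervals. SAP 4.1 and 4.2 test no hypothesis and set no decision rule. Any drift would show in the placebo rows of the ECG tables, in the placebo lines on the mean-change plots, and at zero concentration on the QTcF plot. The primary endpoint is served mainly by the by-treatment summaries and QTc categories (Protocol 9.6.1, SAP Appendix 1), and the interval is an additional display.

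All of that stands. A reader might infer that placebo ECG data go unused, or that the plan reads non-drug shifts as drug effects. The documents support neither. They do leave the reader to subtract by eye, with no measure of uncertainty for the difference. Descriptive status does not explain the gap, because SAP 8.1.8 reports such a difference with an interval in the same study.

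Four narrower points also stand:
- Pulse rate is already placebo-corrected in 8.1.8, so the gap that matters is QTcF and QT.
- Ten minutes of supine rest before each ECG (Protocol 7.1.1.7 and 7.2.1.7) limits posture effects.
- In Part 3 the only post-dose ECG on dosing days is at 1.5 hours (Table E), so the time-of-day argument is weaker there.
- Infusions were lengthened from 60 to 90 minutes after the early Part 1 cohorts (Protocol 1.2.5.1), so pooled IV placebo is not fully matched on procedure.

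**Conclusion.** The point holds as a cheap improvement. The only ECG intervals in SAP 8.1.9 are, as written, on within-arm change. They can mislead if read alone, and the section is out of line with 8.1.8. Because the sentence is defective, a deliberate choice of within-arm change should not be assumed; the intended quantity may have been the 8.1.8 one.

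The size of the problem is unknown. The probabilities above rest on an assumed SD and an assumed shared shift, and they show what could happen rather than what will.

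A reader might also infer that correction costs almost nothing in precision. That is so only for Part 1 IV with pooled placebo, where the half-width grows by about 11% (0.91/0.82). It nearly doubles in the SC cohort and, at 21 vs 7, in Part 3. The Part 2 and Part 3 figures depend on inferred or assumed placebo counts.

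**What to change.** - Repair the sentence in SAP 8.1.9 so that it names the quantity, and limit the interval for change to post-dose time points.
- Add dose-minus-placebo change from baseline for QTcF and QT, and for heart rate for consistency, by dose and time point with a 90% interval.
- Pool placebo across the Part 1 IV cohorts. Compare the SC cohort with its own placebo, and use each Part's own placebo in Parts 2 and 3.
- Note under the Part 1 IV tables that infusion time differed between early and later cohorts.
- Keep the within-arm summaries as supportive.

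The cost is SAP wording and one set of tables and plots from ECGs already scheduled, with no new data. The downside is the wider intervals shown above, which reflect how much placebo information each Part has.

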2.2. Endpoints

2.2.1. Primary Endpoints

Parts 1 and 2

• Incidence, severity and causal relationship of treatment emergent adverse events (TEAEs) and withdrawals due to TEAEs through the end of the study.

- Incidence and causal relationship of treatment emergent serious adverse events (SAEs) through the end of the study.
- Incidence and magnitude of abnormal chemistry, hematology, and urinalysis laboratory findings through the end of the study.
- Abnormal and clinically relevant changes in vital sign parameters through the end of the study.
- Abnormal and clinically relevant changes in electrocardiogram (ECG) parameters through the end of the study.

- Incidence, severity and causal relationship of treatment emergent adverse events (TEAEs) and withdrawals due to TEAEs through the end of the study.
- Incidence and causal relationship of treatment emergent serious adverse events (SAEs) through the end of the study.
- Incidence and magnitude of abnormal chemistry, hematology, and urinalysis laboratory findings through the end of the study.
- Abnormal and clinically relevant changes in vital sign parameters through the end of the study.
- Abnormal and clinically relevant changes in electrocardiogram (ECG) parameters through the end of the study.

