9.6.1. Electrocardiogram (ECG) Analysis

Abnormal and clinical relevant changes for the ECG parameters QT interval, heart rate, QTc interval, PR interval and QRS interval will be summarized by treatment and time.

The number (%) of subjects with maximum post dose QTc values and maximum increases from baseline in the following categories will be tabulated by treatment:

Safety QTc

	Borderline (msec)	Prolonged (msec)
Absolute Value	≥450 - <480	≥480
Absolute Change	30-<60	≥60

In addition, the number of subjects with corrected and uncorrected QT values ≥500 msec will be summarized.

If more than one ECG is collected at a nominal time post dose (for example, triplicate ECGs), the mean of the replicate measurements will be used to represent a single observation at that time point. If any of the three individual ECG tracings has a QTc value \geq 500 msec, but the mean of the triplicates is not \geq 500 msec, the data from the subject's individual tracing will be described in a safety section of the study report in order to place the \geq 500 msec value in appropriate clinical context. However, values from individual tracings within triplicate measurements that are \geq 500 msec will not be included in the categorical analysis unless the average from the triplicate measurements is also \geq 500 msec. Changes from baseline will be defined as the change between QTc post dose from the time-matched average baseline triplicates on Day 0, or the average of the pre-dose triplicate values on Day 1.

Part 3 ECG data analysis will be done as described above.

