6.2.4. ECG

A single or triple 12-lead ECG will be obtained on all subjects at times detailed in the Schedule of Activities given in the protocol. The average of the triplicate readings collected in Part 1 at each assessment time will be calculated for each ECG parameter. Baseline will be defined as the average of the triplicate pre-dose recordings at Day 1, for Parts 2 and 3, the last measurement prior to first dose will be used as the baseline.

The QT, QTc, PR, RR, QRS and heart rate will be recorded at each assessment time.

If not supplied, QTcF will be derived using Fridericia's heart rate correction formula:

$$QTcF = QT / (RR)^{1/3}$$
 where $RR = 60/HR$ (if not provided)

If not supplied, QTcB will be derived using Bazett's heart rate correction formula:

$$QTcB = QT / (RR)^{1/2}$$
 where $RR = 60/HR$ (if not provided)

The maximum increase from baseline will be calculated by first subtracting the baseline value from each postdose measurement to give the change from baseline. The maximum of these values over the respective period will then be selected, except in the case where a subject does not show an increase. In such an instance, the minimum decrease should be taken.

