Appendix 1. Categorical Classes for ECG and Vital Signs of Potential Clinical Concern

Categories for QTcF

QTcF (ms)	450≤ max. <480	480≤ max.<500	max. ≥500
QTcF (ms)	$30 \le \max. \le 60$	max. ≥60	
increase from			
baseline			

[figure not shown]
Categories for PR and QRS

PR (ms)	max. ≥300	
PR (ms) increase	Baseline >200	Baseline ≤200 and
from baseline	and max.	max. ≥50%
	\geq 25% increase	increase
QRS (ms)	max. ≥140	
QRS (ms)	≥50% increase	
increase from		
baseline		

Categories for Vital Signs

Systolic BP (mm Hg)	min. <90	
Systolic BP (mm Hg)	max. decrease ≥30	max. increase ≥ 30
change from baseline		
Diastolic BP (mm Hg)	min. <50	
Diastolic BP (mm Hg)	max. decrease ≥20	max. increase ≥ 20
change from baseline		
Supine pulse rate (bpm)	min. <40	max. >120
Standing pulse rate (bpm)	min. <40	max. >140

Measurements that fulfill these criteria are to be listed in report.

[figure not shown]
CCI			
-			

CCI		
	-	

CCI

[figure not shown]
CCI		

CCI			
CCI			
CCI			

[figure not shown]

CCI

CCI	

CCI						
			I		I	

CCI		

CCI	

CCI

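### Does the SAP lose a safety count by setting the 500 ms threshold for QTcF but not for uncorrected QT?

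*SAP*

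**What the plan says.** Protocol section 9.6.1 sets out the categorical ECG analysis. Besides borderline and prolonged QTc bands, it calls for a summary of "the number of subjects with corrected and uncorrected QT values" at or above 500 ms. It closes with "Part 3 ECG data analysis will be done as described above", so the count applies to the atopic dermatitis cohort too. Section 2.2.1 lists among the primary endpoints "Abnormal and clinically relevant changes in electrocardiogram (ECG) parameters through the end of the study".

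SAP section 8.1.9 says that "ECG endpoints and changes from baseline (QTcF, PR and QRS) will also be summarized descriptively by cohort and treatment using categories" laid out in Appendix 1. The ECG tables there are headed "Categories for QTcF" and "Categories for PR and QRS". The QTcF bands are 450 to below 480 ms, 480 to below 500 ms, and 500 ms or more, with separate bands for increase from baseline. The listing of single post-dose values at or above 500 ends with "msec will also be produced for QTcF".

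Uncorrected QT has a place in section 8.1.9, but without a threshold. Values and changes are summarized by part, cohort, treatment and time. Mean and individual changes are plotted, the latter summaries carry 90% confidence intervals, and the maximum increase over 0 to 12 hours is given for Parts 1 and 2. QTcB is listed only.

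**The concern.** The protocol commits to two counts at 500 ms and the SAP specifies one. ECG abnormality is a primary endpoint, and 500 ms is one of the few numeric ECG criteria the protocol fixes for analysis. A programmer following the SAP literally would produce no table or listing that counts subjects with an uncorrected QT of 500 ms or more. The catch-all listing of values of potential clinical concern does not fill the gap, because Appendix 1 sets no QT criterion. Since the SAP does not declare the omission, a reader cannot tell a decision from an oversight. If the missing count held information that QTcF lacks, the report could omit a safety signal the protocol had promised to show.

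**Working it through.** The question is whether the missing count would tell the reader something that the retained one does not.

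**Inputs.** SAP section 6.2.4 gives Fridericia's "heart rate correction formula": QTcF = QT / RR^(1/3), with RR = 60/HR. The threshold of 500 ms and the bands come from protocol 9.6.1 and SAP Appendix 1. The heart rates below are illustrative; the documents give no heart-rate data.

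**Step 1: where the two counts agree.** Rewrite the formula as QTcF = QT × (HR/60)^(1/3). At 60 bpm or faster the multiplier is at least 1, so QT ≥ 500 implies QTcF ≥ 500. For example, at 70 bpm, 500 × (70/60)^(1/3) = 526.4 ms. All such readings are in the SAP's top band and listing.

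**Step 2: where they differ.** Below 60 bpm the multiplier is less than 1.

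| HR (bpm) | QTcF when QT = 500 ms | Appendix 1 absolute band | QT needed for QTcF = 500 ms |
|---|---|---|---|
| 55 | 485.7 | 480 to <500 | 514.7 |
| 50 | 470.5 | 450 to <480 | 531.3 |
| 45 | 454.3 | 450 to <480 | 550.3 |
| 40 | 436.8 | none | 572.4 |

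At 50 bpm, for instance, a QT from 500 up to 531.3 ms meets the protocol's uncorrected criterion but not the SAP's.

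**Step 3: when a QT of 500 ms reaches no absolute QTcF band.** Solve 500 × (HR/60)^(1/3) = 450: HR = 60 × 0.9³ = 43.7 bpm. The corresponding point for 480 ms is 60 × 0.96³ = 53.1 bpm. So a QT of exactly 500 ms still enters some absolute QTcF band unless the rate is below 43.7 bpm. Even then the increase-from-baseline bands may apply, and Appendix 1 separately flags a supine pulse below 40.

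**Step 4: what the extra readings mean.** The protocol excludes a screening QTc above 450 ms. Taking that as Fridericia, a subject exactly at the limit has an uncorrected QT of 450 × (60/40)^(1/3) = 515.1 ms at 40 bpm. An eligible subject with no change in QTcF can therefore meet the uncorrected criterion simply by having a slow heart rate, on drug or placebo.

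**Step 5: which measure the trial acts on.** Eligibility (exclusion 12 for Parts 1 and 2, exclusion 21 for Part 3) uses QTc. So do the triggers for repeat ECGs, continuous monitoring and cardiology consultation in sections 7.1.1.7 and 7.2.1.7 (500 ms absolute, or 45 ms from baseline). No numeric rule in the protocol uses uncorrected QT, and SAP sections 4.1 and 4.2 set no hypotheses or decision rules.

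**The case for a change.** The strongest case for a change is textual. The protocol's sentence is a firm commitment for two measures, and the SAP fulfils it for one without saying so. Nor can the reference to sponsor reporting standards be assumed to cover the gap. In SAP section 8.1.9 that phrase attaches to the by-time summaries and the 0 to 12 hour maximum, not to the categorical table or the 500 ms listing, and the standards are not in the documents. The table above shows that the QTcF count does not reproduce the uncorrected one below 60 bpm. The remedy would be one table row and one listing from data already collected.

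The mismatch, its silence, and the non-equivalence of the two counts all stand. It does not follow that the plan is deficient. Protocol section 9 allows the SAP to modify the protocol's analysis outline where appropriate, and requires an amendment only for major modifications of primary endpoint definitions or their analyses. The endpoint in section 2.2.1 does not name uncorrected QT. Leaving out one tabulation while keeping the QTcF counts and listing is hard to call major. An added row would mostly record slow heart rates in both arms, and would need heart rate and QTcF beside each value to avoid being misread.

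**Conclusion.** This is a minor inconsistency between protocol and SAP, with no effect on the safety conclusion. The corrected count at 500 ms, which bears on prolonged repolarization, is specified and listed. The two counts can differ only for readings below 60 bpm, and there the difference is the heart-rate correction itself. Uncorrected QT is recorded at every assessment and summarized by time, so an analyst preparing the report can produce the protocol's count or note that QTcF replaced it. Adding it to the SAP would not improve any inference or decision.

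This conclusion assumes that QTcF is the appropriate corrected measure, as the SAP has it, and that uncorrected readings of 500 ms or more at slow rates largely reflect heart rate. The number of subjects involved is not estimated: any figure would depend on assumed distributions of heart rate and QTcF, particularly the lower tail of heart rate, and the documents give neither.
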